**Potential Drug Interactions:**

Periodic monitoring of digoxin levels is recommended during co-administration with lenalidomide.

Monitor patients receiving concomitant warfarin per standard practice guidelines.

Lenalidomide is not a substrate of human CYP enzymes, nor is it an inhibitor or inducer.

**Drug Ordering and Accountability:**

The Revlimid REMS® program provides education and counseling on the risks of fetal exposure, blood clots and reduced blood counts. Counseling will be provided by Biologics, Inc. prior to drug distribution. Please refer to Appendix C (Revlimid REMS® Program). The patient will be required to receive counseling every 28 days during treatment with lenalidomide, follow the pregnancy testing and birth control requirements of the program that are appropriate in order to take the telephone surveys regarding compliance with the program. All physicians must be registered prescribers of Revlimid® in the Revlimid REMS® program. Physician registration

allows access to the Revlimid REMS® software to enroll patients in the Revlimid REMS® program. Please reference Appendix E (Revlimid REMS® Program) and follow the directions for submitting the registration. Biologics, the distributor of the lenalidomide, will not dispense or ship Revlimid® prior to Celgene's receipt of registration. Prescription information **MUST BE** entered using the Revlimid REMS® study specific electronic prescription form found in Appendix C (Revlimid REMS® Program). An authorization **number** must be on the prescription form at the time of faxing. A maximum of a 28-day supply of Revlimid® may be dispensed per cycle sent to the actual address noted on the Revlimid REMS® electronic prescription form. Biologics will verify the authorization number and complete the patient counseling. Patients will be provided with instructions from Biologics with each new dispense on the procedures for return of any un-used Revlimid® capsules.

## CHAPTER 3

### 3. STUDY ENDPOINTS AND DEFINITIONS

#### 3.1. Definition of Disease Progression

Disease progression will be evaluated as defined below and will be evaluated relative to the patient's best response on BMT CTN 0702

**Disease Progression (PD)** from CR or sCR requires one or more of the following:

- A reappearance of serum monoclonal paraprotein, with a level of at least 0.5 g/dL.
- 24-hour urine protein electrophoresis with at least 200 mg paraprotein/24 hours.
- Abnormal FLC levels of >10 mg/dl, only in patients without measurable paraprotein in the serum and urine.
- At least 10% plasma cells in a bone marrow aspirate or on trephine biopsy.
- Definite increase in the size of existing bone lesions or soft tissue plasmacytomas.
- Development of new bone lesions or soft tissue plasmacytomas.
- Development of hypercalcemia (corrected serum Ca >11.5 mg/dL or >2.8 mmol/L) not attributable to any other cause.

**Progressive Disease (PD)** for patients not in CR or sCR, progressive disease requires one or more of the following:

- >25% increase in the level of the serum monoclonal paraprotein, which must also be an absolute increase of at least 0.5 g/dL.
- >25% increase in 24-hour urine protein electrophoresis, which must also be an absolute increase of at least 200 mg/24 hours.
- Absolute increase in the difference between involved and uninvolved FLC levels (absolute increase must be >10 mg/dl), only in patients without measurable paraprotein in the serum and urine.
- >25% increase in plasma cells in a bone marrow aspirate or on trephine biopsy, which must also be an absolute increase of at least 10%.
- Definite increase in the size of existing bone lesions or soft tissue plasmacytomas.
- Development of new bone lesions or soft tissue plasmacytomas.
- Development of hypercalcemia (corrected serum Ca >11.5 mg/dL or >2.8 mmol/L) not attributable to any other cause.
- NOTE: Development of a compression fracture does not exclude continued response and may not indicate progression.

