## 2.4. Study Treatments

### 2.4.1. Lenalidomide

Lenalidomide will be administered initially at the patient's last documented dose prior to discontinuation of BMT CTN 0702 lenalidomide maintenance therapy. Cycle duration is 28 days. Patients will continue lenalidomide until disease progression, or discontinuation due to toxicity, death, or withdrawal from the study. Patients who discontinue lenalidomide due to any reason other than death, or withdrawal of consent will continue to be followed per Section 4.4.1

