## **3.2. Primary Endpoint**

### **3.2.1. Progression-Free Survival**

The primary objective is to compare progression-free survival (PFS) as a time to event analysis between the three randomized treatment arms from the BMT CTN 0702 protocol as a pairwise comparison. The analysis will be conducted once all alive patients have been followed for 5-years post randomization on the BMT CTN 0702 protocol. Patients are considered a failure of the primary endpoint if they die or suffer from disease progression. The time to this event is the time from randomization on the BMT CTN 0702 protocol until progression, death, or initiation of non-protocol anti-myeloma therapy. Patients will be censored at loss to follow-up or end of 2018, whichever comes first.

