4.3 Supplemental Analyses

A supplemental analysis of OS will be included in which OS is analyzed using Cox regression, with treatment arm and risk strata as covariates, and will include demographic and baseline characteristics which are statistically different between treatment arms (p<0.1) for covariates specified in section 3.1. Start time will be randomization on BMT CTN 0702 and all participants randomized on 0702 will be included.

Supplemental analysis of EFS will be included.

- The first will analyze EFS using Cox regression, with treatment arm and risk strata as covariates, and will include demographic and baseline characteristics which are statistically different between treatment arms (p<0.1) for covariates specified in section 3.1. Start time will be randomization on BMT CTN 0702 and all participants randomized on 0702 will be included.
- The second will explore cause-specific hazards for each component of EFS. Cox models
 with treatment arm, risk strata, and demographic/baseline covariates as specified above
 will be used. Start time will be randomization on BMT CTN 0702 and all participants
 randomized on 0702 will be included. For each component, the other components of EFS
 will be considered censoring events.
- The third will analyze EFS using Cox regression in the subset of 0702 participants who initiated lenalidomide maintenance therapy. In this model, the outcome will be the time to

progression or death and the start time will be initiation of maintenance lenalidomide. Discontinuation of lenalidomide maintenance will be considered as a time-varying covariate. Treatment group, strata, and baseline covariates used in the first EFS regression analysis will also be included. The limited interpretation will be noted for this analysis, since it will include non-randomized comparisons and there may be bias in who enrolled in BMT CTN 07LT and continued on lenalidomide maintenance.

Supplemental landmark analyses will be included. The endpoints of PFS, OS, and EFS will be explored in the 0702-enrolled population who is alive four years post randomization (OS) or who is alive and progression- or event-free (for PFS and EFS respectively). A log rank test will compare each outcome for the groups determined by those who were taking lenalidomide at four years post randomization compared to those who were not. Kaplan meier estimates of each outcome at 5 years post randomization will be provided for each lenalidomide status group.

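### Progression on 07LT is judged against the best response on 0702, so patients not in CR/sCR on 0702 whose markers fall further can be dated as progressed later

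*Protocol*

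**What the plan says.** Protocol 3.1 opens by saying that progression is "evaluated relative to the patient's best response on BMT CTN 0702". Two lists follow.

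- **In CR or sCR.** The laboratory criteria are absolute levels. The serum criterion is "A reappearance of serum monoclonal paraprotein, with a level of at least 0.5 g/dL"; urine, free light chain (FLC) and marrow also have fixed cut-offs.
- **Not in CR or sCR.** The same four markers are judged by their increase. The serum criterion is ">25% increase in the level of the serum monoclonal paraprotein, which must also be an absolute increase of at least 0.5 g/dL".

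Both lists also contain criteria that need no paraprotein reference, such as "Development of new bone lesions or soft tissue plasmacytomas" and hypercalcemia.

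Protocol 3.2.1 runs PFS time "until progression, death, or initiation of non-protocol anti-myeloma therapy". Protocol 2.4.1 gives the drug open-ended: "Patients will continue lenalidomide until disease progression, or discontinuation due to toxicity, death, or withdrawal from the study". SAP 1.2.2 allows for a gap between 0702 maintenance and 07LT entry, in which a participant may have taken commercial lenalidomide or another treatment.

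Under SAP 2.2, progression on 07LT is site-reported and not adjudicated. SAP 2.8 plans no sensitivity analyses. Lenalidomide status enters the time-varying Cox models (SAP 4.1 and 4.3) and the four-year landmark analyses, which set "those who were taking lenalidomide at four years post randomization compared to those who were not".

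**The concern.** The reference stops moving when 0702 ends, but treatment and follow-up do not. If a patient below CR on 0702 reaches a lower marker value later, the increase that counts as progression is still measured from the older, higher value. The patient has to regrow past that level first, so biochemical progression is recorded at a higher level and on the same or a later date.

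The list headings add a second problem. Suppose a patient first reaches CR on 07LT. The opening sentence of 3.1 points to the 0702 response and therefore to the increase-based list, whereas the headings can be read as current status and therefore point to the absolute list. Two sites could date the same course differently, and no adjudication on 07LT would bring them into line.

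At stake is the date of the primary endpoint event, and of EFS, in an unknown fraction of patients.

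**Working it through.** **The plan's own figures.** Neither document gives a figure for this effect. The enrolment range reproduces (758 × 0.55 = 416.9, stated as 417; 758 × 0.75 = 568.5, stated as 569), as does the pairwise level (0.05/3 = 0.01667), but neither bears on this point. The inputs that matter are the cut-offs in 3.1.

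**Step 1: serum trigger.** For a reference R in g/dL, the increase-based list is met at about T(R) = max(R + 0.5, 1.25R). The two terms are equal when 0.25R = 0.5, that is at R = 2. If paraprotein has cleared and the CR/sCR list is used, the trigger is 0.5, which equals T(0).

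**Step 2: excess over a trigger based on the later low.** Let B be the best 0702 value and N the lower value reached afterwards.

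- B at or below 2: T(B) − T(N) = B − N, the further fall itself.
- B and N both above 2: T(B) − T(N) = 1.25 × (B − N).
- B above 2 and N below 2: in between. For 3.0 and 1.0 it is 3.75 − 1.5 = 2.25, or 1.125 times the fall of 2.0.
- Already in CR/sCR on 0702: no excess, because the cut-offs are absolute.

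Urine behaves the same way, with the switch at 200/0.25 = 800 mg/24 h. For the FLC difference the excess is simply the further fall.

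**Step 3: illustrative delays.** Assume exponential regrowth, so delay = doubling time × log2[T(B)/T(N)]. Marker values and doubling times are assumptions; the documents give neither.

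| B / N (g/dL) | Trigger as written | Trigger from later low | Doublings | Delay at 2 / 6 / 12 months' doubling time |
|---|---|---|---|---|
| 1.0 / 0.5 | 1.5 | 1.0 | 0.58 | 1.2 / 3.5 / 7.0 |
| 2.0 / 1.0 | 2.5 | 1.5 | 0.74 | 1.5 / 4.4 / 8.8 |
| 1.2 / 0.3 | 1.7 | 0.8 | 1.09 | 2.2 / 6.5 / 13.0 |
| 3.0 / 1.0 | 3.75 | 1.5 | 1.32 | 2.6 / 7.9 / 15.9 |
| 1.0 / 0 (cleared) | 1.5 | 0.5 | 1.58 | 3.2 / 9.5 / 19.0 |

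The last row applies only if the patient stays on the increase-based list after clearing paraprotein.

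**Step 4: illustrative effect on a landmark estimate.** Let f be the share of the on-lenalidomide group with a later low, d the delay in months and h the yearly PFS hazard, all assumed. The rise in that group's 5-year PFS from the 4-year landmark is f × [exp(−h(1 − d/12)) − exp(−h)].

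- Middle case, f = 10%, d = 6, h = 0.15: 0.10 × (0.9277 − 0.8607) = 0.7 percentage points.
- Over f = 5–20%, d = 3–12 and h = 0.10–0.25: 0.1 to 4.4 points.

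**The case against.** The case against a large effect is strong in several places.

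- **Not every cut-off moves.** A reader might infer that all marker criteria in 3.1 depend on the 0702 reference. They do not: the CR/sCR list is absolute, so patients in CR/sCR on 0702 are untouched. This stands.
- **The list may not be frozen.** A reader might infer that the reappearance rule can never apply to someone who clears paraprotein on 07LT. The headings do not say that. The text is ambiguous on this point, and the 1.0/0 example depends on one reading.
- **Deepening is not documented.** Long-term lenalidomide requires three completed years of 0702 maintenance (Protocol 2.3.2) and resumes at the last documented dose, so the 0702 best response already reflects those years. It is tempting to say that dates slip mainly in patients still on lenalidomide. That is plausible, but no figure in either document shows it.
- **Other events may come first.** Lesions, hypercalcemia, death or non-protocol therapy can end PFS before the marker criterion does. This stands for PFS. The cap is less certain in the discontinuation model, whose outcome SAP 4.1 describes as progression or death only.
- **Six-monthly visits may hide a short delay.** True for an individual patient. On average it is not removed: if crossings fall evenly between visits, a 2-month delay moves 2/6 of patients by a whole visit, a mean of 2 months.
- **The exposed analyses already carry a caution.** SAP 4.1 and 4.3 attach one to the PFS and EFS discontinuation models, but on grounds of non-randomized comparison and enrolment bias, not of how progression is measured. The landmark paragraph has no such note.

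**Conclusion.** The point holds for a defined group: patients not in CR/sCR on 0702 whose marker falls further afterwards. For them 3.1 as written raises the laboratory trigger, in serum by 1 to 1.25 times the further fall, and the PFS or EFS date is the same or later. That follows from the text and needs no assumption. Which list applies after a first CR/sCR on 07LT is also left open.

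The size in time is not established. Delays of about 1 to 19 months, and a landmark shift of 0.1 to 4.4 points, rest on assumed marker values, doubling times, shares and hazards.

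A reader might go further and infer that the primary comparison is biased. The documents do not support this. That test compares randomized arms by intent to treat, and all three were planned to receive lenalidomide maintenance. Bias arises only if late deepening differs by arm; otherwise the result is misdated events. Patients who progressed on 0702 keep their adjudicated dates. The PFS and EFS landmarks and the discontinuation Cox models are the most exposed, because they group patients by lenalidomide use.

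**What to change.** For dating the PFS and EFS event only, state in Protocol 3.1 and SAP 2.2 that:

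1. the reference is the lowest confirmed value of each marker since randomization, whether reached on 0702 or 07LT;
2. a patient who reaches CR/sCR on 07LT is from then on assessed with the CR/sCR list.

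If the 0702 reference is kept as primary, add a PFS sensitivity analysis that uses the lowest value to date. This is possible only where marker values were collected: the assessment tables in Protocol 4.4.1 and 4.4.2 do not list them, so availability should be checked first.

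The text change is a sentence or two in each document. Sites would have to carry the lowest value forward, and some PFS times would become slightly shorter. Dates of events during 0702 do not change.

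Because 2.4.1 also uses progression as the point at which lenalidomide ends, the sponsor should reconcile the endpoint definition with that section. No rule for stopping treatment is proposed here.

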## **3.2. Primary Endpoint**

### **3.2.1. Progression-Free Survival**

The primary objective is to compare progression-free survival (PFS) as a time to event analysis between the three randomized treatment arms from the BMT CTN 0702 protocol as a pairwise comparison. The analysis will be conducted once all alive patients have been followed for 5-years post randomization on the BMT CTN 0702 protocol. Patients are considered a failure of the primary endpoint if they die or suffer from disease progression. The time to this event is the time from randomization on the BMT CTN 0702 protocol until progression, death, or initiation of non-protocol anti-myeloma therapy. Patients will be censored at loss to follow-up or end of 2018, whichever comes first.

## **3.3. Secondary Endpoints**

### **3.3.1. Overall Survival**

The event is death from any cause. Overall survival time will be calculated as the time from randomization on the BMT CTN 0702 protocol until death, loss to follow-up or the end of the study, whichever comes first. Patients alive at the time of last observation or lost to follow-up will be censored at the date of last contact. Overall survival will be compared between treatment arms once all alive patients have been followed for 5-years post randomization on the BMT CTN 0702 protocol.

### **3.3.2. Event-free Survival**

Event-free survival (EFS) time will be calculated as the time from randomization on the BMT CTN 0702 protocol until death from any cause, disease progression, or second primary malignancy, whichever comes first. Patients alive at the time of last observation or lost to follow-up will be censored at the date of last contact. Event-free survival will be compared between treatment arms once all alive patients have been followed for 5-years post randomization on the BMT CTN 0702 protocol.

### **3.3.3. Incidence of Second Primary Malignancies**

The event is development of a second malignancy, excluding non-melanoma skin cancers, after randomization on the BMT CTN 0702 protocol. The cumulative incidence of SPMs will be described for all patients enrolled in this long-term follow-up study treating death as a competing risk and censoring patients alive at the time of last observation or lost to follow-up. Incidence of second primary malignancies will be compared between treatment arms once all alive patients have been followed for 5-years post randomization on the BMT CTN 0702 protocol. SPMs will also be described by histologic type.

### **3.3.4. Unexpected Grades 3-5 Adverse Events**

Unexpected grades 3-5 adverse events will be tabulated and compared by treatment arm.

### 3.3.5. Health Quality of Life

The FACT-BMT version 4.0 instrument is comprised of a general core questionnaire, the FACT-G, which evaluates the health-related quality of life (HQL) of patients receiving treatment for cancer, and a specific module, BMT Concerns, which addresses disease and treatment-related questions specific to bone marrow transplant. The FACT-G consists of four subscales developed and normed in cancer patients: Physical Well-being, Social/Family Well-being, Emotional Well-being, and Functional Well-being. Each subscale is positively scored, with higher scores indicating better functioning. The FACT-BMT Total, which is the grand total of all items in the FACT-G and BMT modules, will be used as the outcome measure in summarizing the FACT-BMT data.

The MOS SF-36 instrument is a general assessment of health quality of life with eight components: Physical Functioning, Role Physical, Pain Index, General Health Perceptions, Vitality, Social Functioning, Role Emotional, and Mental Health Index. Each domain is positively scored, indicating that higher scores are associated with positive outcome. This scale has been widely applied in a variety of outcome studies and is being used in this protocol as a generic measure of quality of life. To facilitate comparison of the results with published norms, the Physical Component Summary (PCS) and Mental Component Summary (MCS) will be used as the outcome measures in summarizing the SF-36 data.

HQL will be described and compared between all treatment arms utilizing the FACT-BMT self report, transplant specific questionnaire and the generic quality of life tool (SF-36). The questionnaires will be scored according to standard procedures. The self report questionnaires will be completed yearly until disease progression. Only English and Spanish speaking patients are eligible to participate in the HQL component of this study.

## CHAPTER 4

### 4. PATIENT ENROLLMENT AND EVALUATION

#### 4.1. Enrollment Procedures

##### 4.1.1. Eligibility and Enrollment

All BMT CTN 0702 patients who are alive and progression-free at the completion of the BMT CTN 0702 protocol specified follow-up period are eligible to be followed for long-term outcomes in this protocol. Patients who do not consent to the long-term follow-up mechanism or who have experienced progression on the BMT CTN 0702 study will be followed through the standard CIBMTR long-term follow-up mechanism. Patients who have completed 3 years of 0702 lenalidomide maintenance without evidence of disease progression are also eligible to receive continued, long-term lenalidomide maintenance therapy. Once the study has been described to the patient and informed consent has been obtained, an authorized user at the clinical center completes the 0702 Long Term Follow Up protocol Enrollment form in the Advantage Electronic Data Capture (AdvantageEDCSM) system.

##### 4.1.2. Revlimid REMS® Lenalidomide Counseling

Lenalidomide counseling will be provided through the Revlimid REMS® program for patients who will receive long-term lenalidomide as part of this study. Biologics Inc. will supply all counseling prior to drug distribution. Requirements are outlined in the Study Drug Supply Section 2.7.

#### 4.2. Study Monitoring

##### 4.2.1. Follow-up Schedule

Follow-up visits will occur every 6 months for all patients, beginning from the date of study entry on the long-term follow-up protocol, until death, progression, withdrawal of consent, or the end of the study.

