### 4.4.1. Long-Term Follow-Up Only- Assessment Schedule

Table 4.4.1 summarizes patient clinical assessments over the course of the study for patients who have not progressed prior to enrollment on this study and who are **not** receiving long-term lenalidomide.

The following evaluations will be performed at initiation of long-term follow-up, and then every 6 months (+/-30 days, unless otherwise noted) until progression, death, or withdrawal from the study, unless otherwise noted below:

1. History and physical exam, including height and weight
2. Evaluation for the occurrence of progression every 6 months
3. Evaluation for the occurrence of second primary malignancies
4. Health Quality of Life (HQL) instruments will be completed yearly after randomization on BMT CTN 0702 until disease progression or the end of 2018.
5. *Optional* blood samples for future research will be collected prior to the initiation of long-term follow-up, and at disease progression.

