**Table 4.4.1 – Evaluations During Long-Term Follow-Up**

Study Assessments	Long-term follow-up Assessment Timepoints										
	0	6	12	18	24	30	36	42	R5Y	R6Y	R7Y
History and Physical Examination	X	X	X	X	X	X	X	X			
HQL Instruments 									X	X	X
Optional Blood Samples for Research 	X	Event-driven – at disease progression									

HQL assessments at R5Y, R6Y, and R7Y are a continuation of HQL on BMTCTN 0702. These instruments should be completed yearly from randomization on BMT CTN 0702. There is a +/- 6 month window on HQL assessments to allow for capture at the scheduled 6 month patient visits.

 Optional blood samples will be collected from patients who provided consent prior to the initiation of long-term follow-up and again at disease progression (where applicable).

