#### 5.3. Analysis of the Primary Endpoint

The primary analysis will include all randomized subjects from the BMT CTN 0702 protocol, classified according to their randomized treatment allocation, irrespective of treatment actually received [intent-to-treat]. The time to this event is the time from randomization on the BMT CTN 0702 protocol to progression, initiation of non-protocol anti-myeloma therapy, or death from any cause. Patients will be censored at loss to follow-up or end of 2018, whichever comes first. Deaths without progression are treated as failures no matter when they occur. The analysis will be conducted once all living patients have been followed for 5-years post randomization on the BMT CTN 0702 protocol.

Data for patients not enrolled on the long-term follow-up protocol will be included from the BMT CTN 0702 protocol. Additionally, patients who do not consent to the long-term follow-up or who have progressed on the BMT CTN 0702 protocol will be followed according to the standard CIBMTR long-term follow-up mechanism. The treatment arms will be compared with a two-sided log-rank test stratified on risk status. Tests will be performed pair-wise at the .01667 level in order to maintain study-wide type I error at 0.05. PFS will be compared between treatment arms as a time to event analysis. A secondary analysis of PFS will be conducted using Cox regression, adjusting for demographic and baseline characteristics which are statistically

different between treatment arms ( $p < 0.1$ ). Additionally, discontinuation of lenalidomide maintenance will be considered as a time-varying covariate in the Cox regression model.

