1.2.2 Accrual Plan and Randomization

Participants were eligible to accrue on to BMT CTN 07LT as soon as they finished the earlier of 3 years of maintenance therapy on BMT CTN 0702 or four years of follow up on BMT CTN 0702. The protocol was approved after some participants had already finished 3 years of maintenance on BMT CTN 0702 so they were eligible to enroll when the protocol was activated, and there may have been a period when the participant was on commercially-available lenalidomide or other treatment. The protocol was activated in March 2015, and accrual was targeted through the beginning of 2018 to allow a window of time after the last person enrolled on BMT CTN 0702 would be eligible for BMT CTN 07LT.

Randomization occurred on the parent BMT CTN 0702 trial, which had a 1:1:1 randomization ratio with permuted blocks. Randomization on the parent trial was also stratified by patient risk and center. There was no additional randomization on BMT CTN 07LT.

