2.5 Timing of Analysis

Follow-up for the BMT CNT 07LT protocol continues until the end of 2018; this is approximately when all living patients have been enrolled for 5-years post randomization on the BMT CTN 0702 protocol. The BMT CTN 07LT analysis will begin upon the completion of all data entry and cleaning including retrieval of CIBMTR data after the follow-up is finished.

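### Six-monthly disease evaluations run from 07LT entry with none fixed at study close or year 5, leaving about 3 unassessed months on average before the 31 December 2018 cut-off

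*Protocol*

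**What the plan says.** **Visit clock.** Protocol 4.2.1: "Follow-up visits will occur every 6 months for all patients, beginning from the date of study entry on the long-term follow-up protocol". Protocol 4.4.1 gives the tolerance, "every 6 months (+/-30 days, unless otherwise noted) until progression, death, or withdrawal from the study", and 4.4.2 applies the same rule to patients on lenalidomide. Progression is evaluated every 6 months under both.

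**Tables 4.4.1 and 4.4.2.** Clinical visits are listed at months 0, 6, ... 42 from entry. The R5Y, R6Y and R7Y columns are marked only for the quality-of-life instruments. The footnotes say "HQL assessments at R5Y, R6Y, and R7Y are a continuation of HQL on BMTCTN 0702" and "There is a +/- 6 month window on HQL assessments to allow for capture at the scheduled 6 month patient visits". So R5Y is taken at an existing visit and adds no disease evaluation. No visit is scheduled at study close.

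**Calendar.** Follow-up ends on 31 December 2018 (Protocol 5.2). SAP 1.2.2 gives activation in March 2015 and says "accrual was targeted through the beginning of 2018". Of the end of 2018, SAP 2.5 says "this is approximately when all living patients have been enrolled for 5-years post randomization on the BMT CTN 0702 protocol".

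**Analysis and censoring.** Protocol 5.3 waits for 5 years of follow-up in all living patients and says "Patients will be censored at loss to follow-up or end of 2018, whichever comes first". SAP 4.1 repeats that rule. It uses the last contact date for patients lost on 07LT, and the last CIBMTR progression evaluation for 0702 completers who did not enroll. SAP 1.2.1 and the notes to Exhibit 07LT-3 instead end event-free PFS time at the last myeloma follow-up or data. SAP 4.1 and 4.2 call for 5-year estimates of PFS and EFS.

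**The concern.** The visit clock starts at each patient's own entry date, while the study stops for everyone on one calendar date. Nothing brings the two together, so most patients have their last scheduled disease evaluation some time before the cut-off. The primary endpoint includes progression, which has to be looked for.

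What happens to the gap depends on the censoring rule. If an event-free patient is censored at the end of 2018, the unassessed months count as progression-free. If the patient is censored at the last myeloma data, those months are simply not used. The plan contains both rules. Under SAP 4.1 the credit would go only to 07LT enrollees still in follow-up, because non-enrollees are censored at their last progression evaluation.

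For patients randomized last on 0702, the gap could also fall before year 5, the time point at which PFS and EFS are to be estimated.

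**Working it through.** **1. Reproduce the plan's own figures.** Last nominal visit = entry + 6 × floor((31 Dec 2018 − entry) / 6 months). For entry in March 2015 this is month 42, in September 2018; month 48 would fall in March 2019. That matches the last column of the tables. Even the first entrants are thus last scheduled 92 to 121 days before cut-off. Also 758 × 0.55 = 416.9 and 758 × 0.75 = 568.5, matching the stated 417 and 569. The 55% to 75% range of 3-year PFS is used in step 5.

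**2. What the 30-day tolerance can do.** A visit due by 30 January 2019 may be held by 31 December 2018. Entry on 1 to 30 July 2015 (month 42) or 1 to 30 January 2018 (month 12) is therefore within reach, though nothing requires the early visit. Entry in August 2015 is not: month 36 is August 2018 and month 42 is February 2019. With evenly spread entry, the tolerance reaches about 1 − 5/6 = 17% of patients. Used the other way, it can lengthen a gap to about 7 months.

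**3. Size of the gap.** With entry phase uniform (assumption), the gap is uniform on 0 to 6 months with mean 3, and P(gap > m) = 1 − m/6. That gives 83% over 1 month, 67% over 2 and 50% over 3. A simulation varied the inputs that the documents do not give: last randomization 31 December 2013, 0702 accrual even over 36 to 48 months, 07LT entry at 48 or at 40 to 48 months after randomization, entry delay 0 to 6 months, and tolerance 0 or 1 month.

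| Quantity | Range over scenarios |
|---|---|
| Mean gap | 2.6 to 3.2 months |
| Gap over 1 month | 82 to 90% |
| Gap over 3 months | 37 to 68% |
| Last evaluated before year 5, event-free enrollees | 0 to 10% |
| Same, randomized in the final 6 months | 0 to 59% |

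**4. Who can be last evaluated before year 5.** The last nominal visit is always within 6 months of cut-off, that is, after 30 June 2018. Anyone randomized by about 30 June 2013 has passed year 5 by then (about one month earlier with the tolerance). Taking SAP 2.5 to imply last randomization near 31 December 2013:
- entry exactly 4 years later, 31 December 2017: month 12 is 31 December 2018, at 5.00 years;
- entry 2 January 2018: last nominal visit 2 July 2018, at 4.50 years;
- entry 31 January 2018: last nominal visit 31 July 2018, at 4.58 years.

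The 0% in the table needs everyone to enter exactly at 4 years with no tolerance used. In one scenario, moving the last randomization 3 months earlier cut the share from 6.8% to 1.8%.

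**5. Events in the gap.** Annual hazard h = −ln(3-year PFS)/3, assumed constant; events = n × (1 − exp(−h × 0.25)), with n progression-free at close (assumption).
- n = 300, 75%: h = 0.096, 7.1 events
- n = 350, 66%: h = 0.139, 11.9 events
- n = 400, 55%: h = 0.199, 19.4 events

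**6. The part before year 5.** Take the upper share, 10% of 350 = 35 patients, with h = 0.139. Three unassessed months give 35 × (1 − exp(−0.139 × 0.25)) = 1.2 events; six give 35 × (1 − exp(−0.139 × 0.5)) = 2.4. Over 758 patients that is 0.16 to 0.31 percentage points, and only if the time is credited as event-free.

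**The case against.** The strongest reply is that the SAP already handles this. SAP 1.2.1 and Exhibit 07LT-3 stop the clock at the last myeloma data, so nobody is credited with unassessed months, and what remains is ordinary administrative censoring. That is right under those passages. But Protocol 5.3 and SAP 4.1, the sections that define the primary analysis, give the end of 2018 for patients still in follow-up. One could read that date as an outer limit only; the text does not say so.

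Second, CIBMTR data also feed PFS and EFS (SAP 2.2), and deaths are reported within 24 hours (Protocol 4.3.3). OS is therefore little affected. For progression the help is partial: Protocol 4.1.1 and 4.4.3 assign the CIBMTR mechanism to patients who did not consent or have progressed. For a progression-free enrollee, the 07LT visit is the planned evaluation.

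Third, the visit scheme is the same in all arms, and no effect on the log-rank comparison has been shown. That stands.

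Stronger readings are tempting, and the documents do not support them. A reader might infer that late entrants in general are last evaluated before year 5; this needs late randomization as well as late entry. A reader might take the 7 to 19 events as the error in 5-year PFS; most of that time lies after year 5. A reader might think that patients censored before year 5 drop out of the 5-year estimate; Kaplan-Meier uses them until they are censored. Nor does the plan claim exact 5-year follow-up for all: SAP 2.5 calls the end of 2018 approximate, and SAP 2.8.1 restates the trigger as 5 years or the end of 2018.

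**Conclusion.** The point holds in limited form. No closing or 5-year disease evaluation is scheduled, and under evenly spread entry the last scheduled evaluation precedes cut-off by 0 to 6 months, about 3 on average. The 7 to 19 events in the whole gap rest on assumed numbers at risk and a constant hazard. They fall mostly after year 5 and should be similar across arms.

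The effect on 5-year PFS is small: about 1 to 2 events, or 0.2 to 0.3 points, at the upper end of a 0 to 10% share that depends on randomization dates the documents do not give. Censoring at the end of 2018 turns the gap into slightly optimistic PFS; censoring at the last myeloma data costs only precision. This is a cheap improvement worth making, not a threat to the primary comparison.

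**What to change.** 1. In Protocol 4.2.1 and Tables 4.4.1 and 4.4.2, add a closing disease-status evaluation between 1 October and 31 December 2018, covering progression, new anti-myeloma therapy, second primary malignancy and vital status. Use a visit already falling in that window, or bring the next one forward. Place it on or after the patient's 5-year date where possible.
2. Reconcile Protocol 5.3 and SAP 4.1 with SAP 1.2.1 and Exhibit 07LT-3, so that event-free patients are censored for PFS at the last disease evaluation on or before 31 December 2018.

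The longest gap then falls from 6 months (7 with the tolerance) to the 3-month width of the window. An evaluation held at the cut-off itself would put every patient randomized by 31 December 2013 at 5.0 years or later, against a minimum of about 4.4 to 4.5 years now.

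The cost is protocol and SAP wording, a shorter last interval, and for some patients one in-study visit that would otherwise have fallen in early 2019. This applies equally in all arms.
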